Therefore, we created Enhanced Medical Rehabilitation (EMR) for older adults. A real-world adaptation of the science of behavior change, EMR is an integrated set of skills for physical and occupational therapists (PT/OT) that transform standard post-acute rehabilitation through: (1) a patient-directed, interactive approach (2) increased rehabilitation intensity (3) frequent feedback to patients on effort and progress. We developed training and supervision techniques so that PT/OTs carry out these skills with high treatment integrity.

In NIMH R34 pilot work, we found: (1) EMR is high-intensity and engaging: therapy by PT/OTs trained and supervised in EMR is greatly amplified in intensity and patient engagement compared to standard-of-care rehabilitation. (2) EMR improves functional and affective recovery: patients randomized to EMR had better improvement of function, physical performance, and positive and negative affect. (3) EMR overcomes barriers to rehabilitation: patients with depressive symptoms, cognitive impairment, and multiple medical comorbidities benefitted most from EMR relative to standard therapy.

We propose a randomized trial that will test EMR's benefits over standard-of-care rehabilitation for affective and functional recovery. Our aims are (1) examine the effectiveness of EMR for improving functional and affective outcomes in 252 older adults admitted to SNFs for post-acute rehabilitation, and (2) examine EMR's ability to overcome patient-level barriers (such as depression) to successful rehabilitation.

The innovation of this project is high: it is a novel application of theories of behavior change to improve both affect and function. It responds to NIMH strategic plan objective 3, "Develop new and better interventions for mental disorders that incorporate the diverse needs and circumstances of people with mental illness."

The public health significance is also high: recovery from disablement is a health issue of enormous human and economic significance. Success in this line of research will make rehabilitation more effective. Doing so would benefit all older adults in this sector of care but particularly those with depression, cognitive impairment, and other complications. This project addresses NIMH's goal of interventions to improve mental health and related health outcomes in real-world settings.

A2 Study Aims and Hypotheses

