H1: EMR will improve functional and affective recovery to a greater extent than standard-of-care rehabilitation.

Explanation of H1: The purpose of H1 is to examine the effectiveness of EMR. If H1 is supported, this could establish EMR as the gold-standard practice for post-acute rehabilitation. Our primary analysis is the change from baseline to Day 30. This single primary endpoint allows for an effectiveness test that is not confounded by length of stay differences or post-discharge issues beyond the reach of EMR.

C2 Secondary Aim

Aim 2: Examine EMR's ability to overcome patient-level barriers to successful rehabilitation.

H2: The effectiveness of EMR for functional recovery will be greatest in: (a) patients with clinical depression; (b) patients with high levels of medical comorbidity; (c) patients with cognitive impairment.

Explanation of H2: EMR was designed to overcome barriers to rehabilitation (for example, due to depression); therefore, the difference in functional recovery between EMR and SOC should be greater in the most vulnerable older adults. If H2 is supported, we will demonstrate that older adults with these common comorbidities benefit the most from high intensity, high engagement rehabilitation. If so, this would refute conventional wisdom in post-acute rehabilitation, codified in admission criteria for rehabilitation facilities, regarding the appropriate candidates for rehabilitation (as described in Significance).³²

C3 Rationale for the Selection of Outcome Measures

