Rating Scale, a commonly-used depression measure in clinical trials. We have used it in many prior studies of older adults. Our secondary measure is an 18-item positive and negative affect scale that measures positive and negative (depressed and anxious) affect. It measures the dominant dimensions of human emotional experience, which have important roles in both quality of life and as a predictor of success in geriatric rehabilitation. It is a combination of the full 10-item positive affect scale of the Positive and Negative Affect Schedule (PANAS),⁷⁷ plus five items from the brief PANAS measuring negative affect⁷⁸ and the three non-reverse coded items from a brief State Anxiety Scale⁷⁹ derived from the State Trait Anxiety Inventory to measure negative (anxious) affect. This scale uses participants' responses to questions (e.g., "how anxious do you feel at present") to assess their current feeling or affective states. The PANAS has excellent reliability in post-acute rehabilitation, where it is considered valuable in capturing the range of mood and motivational issues in this setting.⁸⁰ Our addition of specific anxiety items reflects the high rate of anxiety problems in post-acute rehabilitation.^{29,81-84} Additionally, this dimensional assessment of affect responds to calls by NIMH to use as outcomes dimensions that reflect more basic, validated emotional or behavioral states, as reflected in the Research Domain Criteria.⁸⁵ These depression/affect measures will only be carried out in participants with a baseline clinical diagnosis of current major or minor depressive episode, based on the Structured Clinical Interview for DSM-IV (SCID)⁸⁶ which we will carry out at baseline prior to randomization. We have considerable experience with the SCID in this population from prior NIMH-funded studies. Based on our pilot RCT experience, about 25% of eligible participants will have a current diagnosis; we will enrich the sample by continuing to recruit to ensure that 50% of randomized participants have a depression diagnosis, so that this study is adequately informative regarding benefits for late-life depression in this setting. Our test-retest Kappa (using different, blinded raters) for major/minor depression in this setting is 0.8 (good).

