After checking in with facility patient-care staff to confirm the availability of the potential participant, patients who appear appropriate per chart will be approached by WU research staff and told that they may be eligible for the enhanced rehabilitation study. To ensure participants' comfort, the study team will assess the setting and ensure that the individual is positioned such that they can comfortably complete any assessments, including writing in a reasonable position, that they have had an opportunity to go to the toilet, eat and are dressed (if appropriate). Just asking the participant may not be the best approach for all individuals as some may agree without actually feeling this it is the best time or situation. It is important that participants not put off their own needs (whether it be repositioning themselves, using the bathroom or getting dressed) and that the research assessments not interfere with this.

If the patient gives their assent, research staff will screen them for cognitive impairment, with the Short Blessed Test (SBT). If they do not assent to the screening then we will not ask them the questions and will not contact them further.

Patients who score 13 or higher will be assumed unable to provide consent and thus will be excluded from the study. Study staff and/or PI will use clinical judgment to determine whether to include patients who score between 10 and 12 on the SBT. If they are not cognitively impaired (score 0-9 on SBT) at the time of this screening we will go through the full informed consent process for the study.

Research staff will review the consent form with the patient in their room at the skilled nursing facility, encouraging the patient to ask questions throughout. The assessment of understanding tool will be used as needed to ensure each patient understands the procedures, risks, and benefits of the study.

2.d Randomization Method and Blinding

We will randomize 1:1 to EMR (i.e., all OT/PT sessions done by EMR-trained and supervised therapists) or SOC (i.e., all sessions done by non-EMR-trained therapists), as in our pilot RCT. We will stratify by SNF site and by baseline depression status. To prevent subversion of randomization,⁶¹ the statistician will hold the randomization list, releasing an assignment once a participant is consented and eligible.

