
Our sample size is based on 80% power to detect a Cohen's $d=0.4$ effect size on the ANCOVA difference in treatments at day 21, based on a two-tailed $p<0.025$ (because two outcome measures are used). G*Power 3.1.2 was used for power calculations. A Cohen's $d=0.4$ is between "small" (0.2) and "medium" (0.5) effect sizes. Effect sizes for function were in the "large" range, $d=0.7-0.9$, but we acknowledge that these observed

effect sizes are qualified by the small sample size, and it makes most sense to be more cautious regarding likely effect sizes in a full-scale study, hence our choice to power at $d=0.4$. Such an effect size is clinically relevant for the functional outcomes.³ *We will only examine affective recovery as an outcome for those who are “affectively impaired” to begin with; i.e., those with clinical depression at baseline; with this reduced N, we are powered at 80% for a $d=0.54$. This same power analysis would apply for any subgroup analysis of depressed; i.e., if we wish to demonstrate that EMR is effective both in the case of clinical depression and in “non-depressed” older adults.*

G2 Interim Monitoring and Early Stopping

Not applicable; we do not have any interim data analysis or early stopping plans.

G3 Analysis Plan

The continuous demographic and clinical variables at baseline will be compared between the EMR group and the SOC group using the Two Independent Sample t Test or the Wilcoxon Two Sample Test, whichever is appropriate. Baseline categorical variables (e.g., race) will be compared between the groups using either the Chi Square Test or Fisher’s Exact Test, whichever is appropriate. We will examine data descriptively using crosstabulations, histograms, and tests for normality (with corrective actions, data transformation or nonparametric alternatives, as needed). An analysis-appropriate technique will handle missing data.

G4 Statistical Methods

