2. PROMIS (Ability to Participate in Social Roles and Activities).
3. OARS IADL.

Process data: Measures of the dosage of intervention (# of EMR steps done in each therapy activity; PAT %; Rehab Participation Scale Score) before and after training.

Study Methods:

i. Trial Design:

This was a randomized, parallel-group trial where patients received either EMR or SOC therapy.

Patients who received EMR received therapy only from therapists who were trained and supervised in EMR. Their therapy sessions followed the EMR protocol. Otherwise, their SNF care did not differ from usual care.

Patients who received SOC received therapy only from PT/OTs (or assistants) who were not trained nor supervised in EMR. These therapists were monitored (videotaped or observed) but were not asked to do anything differently with their patients.

ii. Randomization:

Randomization (blocks...2 and 4 patients). was 1:1 to EMR or SOC with stratification by SNF site and by baseline depression status.

iii. Sample Size:

The sample size was based on 80% power to detect a Cohen's $d=0.4$ effect size on the ANCOVA difference in treatments at primary endpoint, based on a two-tailed $p<0.025$ (because two outcome measures are used). G*Power 3.1.2 was used for power calculations. A Cohen's $d=0.4$ is between "small" (0.2) and "medium" (0.5) effect sizes. Effect sizes for function were in the "large" range, $d=0.7-0.9$, but we acknowledge that these observed effect sizes are qualified by the small sample size, and it makes most sense to be more cautious regarding likely effect sizes in a full-scale study, hence our choice to power at $d=0.4$. Such an effect size is clinically relevant for the functional outcomes. *We will only examine affective recovery as an outcome for those who are "affectively impaired" to begin with; i.e., those with clinical depression at baseline; with this reduced N, we are powered at 80% for a $d=0.54$. This same power analysis would apply for any subgroup analysis of depressed; i.e., if we wish to demonstrate that EMR is effective both in the case of clinical depression and in "non-depressed" older adults.*

iv. Statistical Interim Analyses/Stopping Guidance:

Not applicable; we did not have any interim data analysis or early stopping plans.

v. Timing of Final Analysis:

All outcomes will be analyzed collectively.

vi. Timing of Outcome Assessments (including windows):

	Schedule of Assessments	SNF admit (baseline)	Day 7	Day 30	SNF discharg e	Day 60	Day 90

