The primary measure employed for assessing functional improvement will be The Barthel Index. This index is a 10-item scale used to ascertain the degree of independence of normal daily activities. This will be done by taking the sum of these 10 items. A high score indicates a high degree of independence, and a score can range from 0 to 100.

- 2) Aim 2: Examine EMR's ability to overcome patient-level barriers to successful rehabilitation.

H2: The effectiveness of EMR for functional recovery will be greatest in: (a) patients with clinical depression; (b) patients with high levels of medical comorbidity; (c) patients with cognitive impairment.

Part (a) will be assessed using the MADRS, which is a 10-item scale used to assess for major depression. Each item is rated on a scale of 0 to 6, where a 6 is worse. The total score (i.e., sum of these 10 items) will be

used to assess for major depression and can range from 0 to 60.

Part (b) will be assessed using the CIRS-G, which is a 13-item scale used to assess for disease in all major body systems. Each item is rated on a scale of 0 to 4, with a 4 indicating severe impairment. The total score (i.e., sum of these 10 items) will be used to assess for medical comorbidity and can range from 0 to 52.

Part (c) will be assessed using the SBT Scores. The SBT is a 6-item scale used to assess for memory/concentration deficits. A total score, which is obtained after applying a weighting factor to each item then summing up the final item scores, can range from 0 to 28. A high score indicates impairment consistent with dementia.

ii. Analysis Methods

The primary outcome analysis for functional recovery will use a marginal model with time (baseline and discharge), condition (E-MR vs. SOC) and time x condition as fixed effects and with a covariance structure specified based on the Bayesian Information Criterion (BIC). Employing a marginal model allows for a more robust approach in the handling of missing data compared to the traditional ANCOVA model.

For H2 under Aim 2, each potential continuous moderator will be individually inserted into the primary model. The term of interest will be the time x condition x moderator interaction.

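### The 80% subgroup power at d=0.54 is for one subgroup test; showing benefit in both depressed and non-depressed patients has about 60–64% power at the planned size

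*Protocol*

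**What the plan says.** Protocol section G1 sizes the trial for 80% power at d=0.4, two-sided alpha 0.025. For the half of the sample with clinical depression at baseline it gives 80% power at d=0.54. It then extends that figure: "This same power analysis would apply for any subgroup analysis of depressed; i.e., if we wish to demonstrate that EMR is effective both in" those with clinical depression and those without. The SAP (Study Methods, iii. Sample Size) keeps the statement: "This same power analysis would apply for any subgroup analysis of depressed". Neither document gives any other power figure for subgroups.

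The hypothesis about depression as a modifier is H2(a), in Protocol section C2 and SAP Objectives: "The effectiveness of EMR for functional recovery will be greatest in: (a) patients with clinical depression". The SAP (Analysis, ii. Analysis Methods) tests it by adding each moderator as a continuous variable: "The term of interest will be the time x condition x moderator interaction". For part (a) the moderator is the MADRS total score.

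**The concern.** A power for one two-arm comparison has been carried over to a goal that needs two comparisons to succeed. Showing that EMR works in depressed patients and also in non-depressed patients fails if either test fails, so its power must be lower than that of either test alone. The question of whether the effect is larger in the depressed is different again, because it concerns a difference between two effects.

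Interpretation is at stake. Both documents say that support for H2 would overturn accepted views on who is a suitable candidate for rehabilitation. A reader who believes that subgroup analyses carry 80% power at d=0.54 could take significance in only one subgroup as evidence that the effect differs, or a null interaction as evidence that it does not. The design does not support either inference, even with full recruitment and complete data.

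**Working it through.** **Inputs**
- Planned size: "252 older adults admitted to SNFs for post-acute rehabilitation" (Protocol, introductory summary).
- Depression share: recruitment continues to "ensure that 50% of randomized participants have a depression diagnosis" (Protocol C3), so 126 depressed and 126 non-depressed.
- Allocation: "We will randomize 1:1 to EMR" and "We will stratify by SNF site and by baseline depression status" (Protocol E2, 2.d), so 63 per arm in each subgroup.
- Two-sided alpha: 0.025 in the power sections of both documents. The SAP's general significance level is 5%, so both are shown.
- No dropout allowance is stated, and none is applied.

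**Step 1: reproduce the plan's figures.** By normal approximation, power = Φ(d·√(n/2) − z), with n per arm and z = 2.241 (alpha 0.025) or 1.960 (alpha 0.05).
- Whole trial: 0.4 × √63 = 3.175; Φ(3.175 − 2.241) = 82.5% (82.1% by noncentral t). This agrees with the stated 80%.
- Depressed half: 0.54 × √31.5 = 3.031; Φ(3.031 − 2.241) = 78.5% (77.6% by noncentral t). This is close to the stated 80%. At alpha 0.05 it would be 85–86%, so 0.025 is the alpha behind the plan's figure.

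The 80% is therefore the power of a single test in a single subgroup of 126.

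**Step 2: power for both subgroups.** The subgroups contain different patients, so the two tests are independent and joint power is the product.

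| Two-sided alpha | True d in each subgroup | One test (noncentral t) | Both tests |
|---|---|---|---|
| 0.025 | 0.54, plan's nominal figure | 80% | 0.80² = 64% |
| 0.025 | 0.54, recomputed | 77.6% | 0.776² = 60% |
| 0.05 | 0.54 | 85.3% | 0.853² = 73% |
| 0.025 | 0.40 | 49.2% | 0.492² = 24% |
| 0.05 | 0.40 | 60.6% | 0.606² = 37% |

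Joint power of 80% would need each test to have √0.80 = 89%.

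**Step 3: the interaction, as illustration only.** Take a binary moderator with four cells of 63. In SD units the standard error of the difference between the two subgroup effects is √(4/63) = 0.252, against √(2/63) = 0.178 within one subgroup.
- Interaction of 0.54 SD: 0.54/0.252 = 2.143. Power is Φ(2.143 − 1.960) = 57% at alpha 0.05, or Φ(2.143 − 2.241) = 46% at alpha 0.025.
- Interaction of 0.8 SD (0.8 in the depressed, 0 in the rest, averaging the design effect of 0.4): 0.8/0.252 = 3.175, giving 89% at alpha 0.05 or 82% at alpha 0.025.

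**The case against.** The best defence is that the sentence means each subgroup test, taken separately, has the stated power. On that reading it is about right at a 50/50 split: 78% against 80%. The plan never writes that joint power is 80%, and the statement is conditional on what the team may wish to show. This stands in part. However, the sentence explains itself as demonstrating an effect in both groups, which is a conjunctive goal, and no other subgroup power is offered. The separate reading narrows the fault but does not remove it.

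Two stronger readings are tempting and should be resisted.
- A reader might infer that the plan claims 80% power for H2(a). It does not. The sentence concerns effectiveness within each subgroup, and neither sample-size section mentions H2, moderation or an interaction. The missing interaction power is an omission.
- A reader might take 57% as the most power the interaction could have. It is the power for one assumed size at one alpha. An interaction of 0.8 SD would have 82–89%, and the pilot effects on function quoted in G1 were d=0.7–0.9. Nor does the four-cell calculation describe the SAP's test directly: power with continuous MADRS depends on its distribution and slope, which the documents do not give.

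It can also be said that the planned split never materialised, since the SAP's Objectives record only 14 participants with a depression diagnosis. That makes the figures above a best case for subgroups defined by diagnosis. It does not correct the sentence, which the SAP retains alongside H2(a).

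**Conclusion.** The concern holds for the conjunctive goal. The plan attaches the power of a single subgroup test to showing benefit in both subgroups. With d=0.54 in each, the real figure is about 60–64% at the plan's alpha of 0.025, which is 16 to 20 points below the stated 80%; at alpha 0.05 it is about 73%. At d=0.4 in each subgroup it is 24% (37% at alpha 0.05).

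On H2(a) the conclusion is limited: the stated calculation does not cover the interaction, and no power for it has been given.

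The figures assume an exact 126/126 split, 1:1 allocation within each half, equal SDs, effect sizes already on the covariate-adjusted scale, and no missing data. Dropout would lower all of them. The error lies in the stated power and how results may then be read; the overall sample size reproduces and is not in question.

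**What to change.** Replace the sentence in Protocol G1 and in SAP Study Methods iii with wording to this effect:

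> At the planned 126 depressed and 126 non-depressed patients, power is about 80% at d=0.54 (two-sided alpha 0.025) for each subgroup test taken separately. Power for both tests to succeed, with d=0.54 in each, is about 60–64%. This calculation does not cover the interaction that tests H2(a).

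In SAP Analysis ii, add that the interaction estimate will be reported with its 95% CI. Add also that significance in only one subgroup will not be taken as evidence of moderation, nor a non-significant interaction as evidence of its absence. If an interaction power is quoted, label it as an illustration for a balanced binary moderator and state the assumed size and alpha; do not present it as the power of the continuous MADRS test.

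The cost is a few sentences and a less favourable stated power. Enrolment and the planned models do not change.

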Time course analyses will be conducted to investigate the differences between pre and post outcome measures. These analyses will be used to ascertain whether there is a statistically significant difference in change over time between the EMR group and the SOC group, controlling for baseline values. Analyses of the outcome measures for normality will be carried out. Time course analysis techniques such as mixed effects models, t test of the differences, Wilcoxon test of the differences, or ANCOVA on the differences (using baseline value as the covariate) will then be conducted, depending on the normality tests. Our favored method for the primary analysis of baseline to day 30 (i.e., pre-post treatment) effects is the ANCOVA approach, comparing the EMR and standard-of-care groups in change scores, covarying for baseline scores. This approach is recommended as the superior and most well-powered approach for examining pre-post RCT data.⁹¹ Our tests of the pilot data agreed with this: the ANCOVA approach had as much or more statistical power than other approaches (t-test, Wilcoxon, mixed-effect model) for all outcomes.

Participants will be randomized within each facility (i.e., stratified by facility) and then receive a PT/OT therapist pair who either is or is not trained/supervised in EMR based on randomization assignment. Thus participants are nested within therapists and therapists are nested within facilities. This multi-stage nested (hierarchical) design structure introduces possible correlation of participant outcomes with therapist. Such classification effects (facility/therapist) will be analyzed using Proc Nested in SAS or with the multi-level modeling available in Mplus that deals with stratification, clustering, and weighting.

We will also examine all time points to Day 90, to provide a real-world estimate of EMR and improve power to detect important secondary outcomes such as rehospitalization and institutionalization. We acknowledge these data may become somewhat naturalistic

in a rehabilitation population, given differences in length of stay, transfers to different facilities, and re-hospitalizations. Mixed effects models are the preferred method for these multiple-time-point analyses, especially as some missing data are to be expected post-discharge.⁹²

H Data Handling and Record Keeping

H1 Confidentiality and Security

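### Protocol G4 makes the choice of outcome test depend on unspecified normality tests, and the SAP removes that rule for the Barthel Index without restoring the baseline-adjusted analysis on which the trial was powered.

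*Protocol*

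**What the plan says.** Protocol G4 says the outcome measures will be examined for normality. It then offers mixed models, a t test of the differences, a Wilcoxon test of the differences, "or ANCOVA on the differences (using baseline value as the covariate) will then be conducted, depending on the normality tests". It does not name the normality test or its level, say whether raw scores, changes or residuals are tested, or say which result leads to which method.

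The next sentences of G4 call ANCOVA on change, with baseline as covariate, the favoured method for the primary baseline-to-day-30 comparison, and add: "This approach is recommended as the superior and most well-powered approach for examining pre-post RCT data". Earlier in the same paragraph G4 says the arms will be compared with control for baseline values.

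G1 states power for that method alone, as an "effect size on the ANCOVA difference in treatments", "based on a two-tailed $p<0.025$ (because two outcome measures are used").

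SAP version 2 (Analysis, ii. Analysis Methods) names a single model for the Barthel Index: a marginal model at baseline and discharge with terms for time, condition and their interaction, and a covariance structure chosen by BIC. There is no normality condition. The stated reason for leaving ANCOVA is missing data. The SAP's sample-size text still rests on ANCOVA at 0.025, while its Statistical Principles set the significance level at 5%.

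**The concern.** A primary test should be fixed before outcomes are seen. G4 states a preference, but the sentence before it leaves the method to a check on the outcome data that has no operating rule. An analyst could fit any of the four methods and claim to have followed the protocol.

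Two things are at stake. The first is power: the one nonparametric option listed works on unadjusted change and so discards the baseline adjustment that G4 itself calls best powered. The second is the false-positive rate, if the freedom is used after results are known. The gate buys nothing in return, because with about 126 per arm ANCOVA does not need a normal outcome to hold its level.

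The SAP settles which model is used for the Barthel Index. The question that remains is whether that model is the baseline-adjusted analysis for which power was claimed.

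**Working it through.** **Inputs.** Total size: "in 252 older adults admitted to SNFs for post-acute rehabilitation" (protocol opening summary). Allocation: "We will randomize 1:1 to EMR" (Protocol E2, 2.d), so n = 126 per arm. Power and effect: "Our sample size is based on 80% power to detect a Cohen's $d=0.4$ effect size on the ANCOVA difference" (G1). Two-sided alpha is 0.025 (G1). The documents give no baseline-to-follow-up correlation r and no Barthel distribution. I assume r = 0.3 to 0.7 and, for the simulations, scores in 5-point steps limited to 0–100.

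**The plan's own figure.** For d = 0.4, alpha 0.025 and 80% power, the required total is 238 (normal approximation), 242 (t) or 241 (ANCOVA F test). At N = 252, power is 82.5%, 82.1% and 82.1%. The stated 80% is therefore met with a small margin. An assumed 5% dropout would give 251–255, but no dropout rate is stated. The gap does not affect this point.

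**Cost of dropping the baseline adjustment.** Power ≈ Φ(d_eff·√(n/2) − 2.241), with √(126/2) = 7.937.

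- ANCOVA, d in residual SD units: 0.4 × 7.937 − 2.241 = 0.934, giving 82%.
- Unadjusted change: the residual SD is √(1 − r²) and the change SD is √(2(1 − r)), so d_eff = 0.4·√((1 + r)/2).
- Wilcoxon on change: multiply that d_eff by √(3/π) = 0.977.

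| r | d_eff, change | t test on change | Wilcoxon on change | ANCOVA |
|---|---|---|---|---|
| 0.3 | 0.322 | 62% | 60% | 82% |
| 0.5 | 0.346 | 69% | 67% | 82% |
| 0.7 | 0.369 | 75% | 73% | 82% |

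Put another way, 252 participants analysed by unadjusted change are worth 252 × (1 + r)/2 = 164, 189 or 214 analysed by ANCOVA.

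If d = 0.4 is instead in raw day-30 SD units, ANCOVA has 86%, 92% and 99% power for r = 0.3, 0.5 and 0.7. Wilcoxon on change has 65%, 80% and 96%. The direction is the same.

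**The SAP model.** With both visits observed, separate arm means at each visit make the mean structure saturated. The interaction estimate is then the difference in mean change, with the variance of change. That is the t-test column: 62–75%. At the SAP's 5% level, 2.241 becomes 1.960. Change then gives Φ(0.600) = 73%, Φ(0.790) = 79% and Φ(0.967) = 83%, against 89% for ANCOVA.

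**False-positive rate.** I simulated 10,000 null trials per scenario with 126 per arm and r = 0.5. Baseline mean/SD to follow-up mean/SD was 45/15 to 65/18, 50/18 to 78/20, and 55/18 to 88/20. Nominal level is 2.5%.

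| Procedure | Rejection rate across scenarios |
|---|---|
| ANCOVA, fixed | 2.46–2.59% |
| Wilcoxon on change if Shapiro-Wilk on change has p < 0.05, otherwise ANCOVA | 2.45–2.64% |
| Best p-value of ANCOVA, t and Wilcoxon | 4.0–4.6% |

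**How often a gate would trip.** In 1,500-run simulations of bounded scores, Shapiro-Wilk at 0.05 rejected raw day-30 scores in 100% of runs, change scores in 44–99% and ANCOVA residuals in 9–100%, depending on scenario. The answer turns on which quantity is tested, and G4 does not say.

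**The case against.** The strongest reply has three parts.

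First, G4 names ANCOVA as favoured for this very comparison straight after the conditional sentence, and nowhere says that failed normality leads to Wilcoxon. This stands. A reader might infer that the Barthel Index would almost always fail and that ANCOVA would therefore be replaced. The documents do not support that: no mapping is given, and only raw scores failed consistently, under assumed distributions. The defect is an unresolved conflict between two adjacent statements.

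Second, a gate need not inflate error. This also stands. The 4.0–4.6% arises only if the best of three results is picked, which G4 does not authorise but also does not prevent.

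Third, the SAP replaces the rule with one ungated model for the Barthel Index, and gives missing data as its reason. That settles the choice of test for this outcome. It does not restore the powered analysis, because the model has no baseline covariate and lets the baseline means differ by arm.

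The SAP already reports SCID counts, so it was finalised after some study data were known. A reader might infer that its model was chosen from the results. The documents do not show this: the SCID is a baseline measure, and nothing indicates that outcome comparisons had been seen.

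The similar wording in G3 sits in a sentence on descriptive examination, and this point does not rest on it.

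**Conclusion.** The point holds in a limited form. G4 leaves the test open to an undefined check on the outcome data while favouring ANCOVA. That permits a weaker test (about 60–73% power against 82%) and leaves room for selection after the fact (up to about 4.0–4.6% against 2.5%). It mandates neither.

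For the Barthel Index, the more practical consequence lies in the SAP. Its model costs about as much power as an unadjusted change comparison: 62–75% against 82% at alpha 0.025, or 73–83% against 89% at 5%.

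The power figures assume complete data, r between 0.3 and 0.7, and d = 0.4 in residual SD units. On the raw-SD scale the loss is smaller, especially at high r. The false-positive figures rest on assumed Barthel distributions. The validity of the SAP model's estimate is not in question; only its precision is.

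**What to change.** In Protocol G4, delete the clause that conditions outcome comparisons on normality tests. In both the protocol and the SAP, state one baseline-adjusted primary Barthel analysis, used whatever the distribution. Either of these would do:

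- ANCOVA with baseline as covariate.
- A longitudinal model with baseline as covariate, or with the baseline mean constrained equal across arms. The constrained form keeps the SAP's handling of missing data most directly, since a participant with only one of the two scores still contributes.

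Keep normality checks as diagnostics, and label any rank-based analysis as sensitivity.

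The cost is a few sentences in G4 and the SAP, with no new data or visits. If the analysis has already been run, report when the model was fixed and show the baseline-adjusted estimate beside the SAP result.
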